10.3. Appendix 3: Contraceptive Guidance and Collection of Pregnancy Information

Definitions:

Woman of Childbearing Potential (WOCBP)

A woman is considered fertile following menarche and until becoming post-menopausal unless permanently sterile (see below).

If fertility is unclear (e.g., amenorrhea in adolescents or athletes) and a menstrual cycle cannot be confirmed before first dose of study intervention, additional evaluation should be considered.

Women in the following categories are not considered WOCBP

1. Premenarchal
2. Premenopausal female with one of the following:
 - Documented hysterectomy
 - Documented bilateral salpingectomy
 - Documented bilateral oophorectomy
 - For individuals with permanent infertility due to an alternate medical cause other than the above, (e.g., Mullerian agenesis, androgen insensitivity), investigator discretion should be applied to determining study entry.

Note: Documentation can come from the site personnel: review of the participant's medical records, medical examination, or medical history interview.

3. Postmenopausal female
 - A postmenopausal state is defined as no menses for 12 months without an alternative medical cause.
 - A high follicle stimulating hormone (FSH) level in the postmenopausal range may be used to confirm a postmenopausal state in women not using hormonal contraception or hormonal replacement therapy (HRT). However, in the absence of 12 months of amenorrhea, confirmation with more than one FSH measurement is required.
 - Females on HRT and whose menopausal status is in doubt will be required to use one of the non-estrogen hormonal highly effective contraception methods if they wish to continue their HRT during the study. Otherwise, they must discontinue HRT to allow confirmation of postmenopausal status before study enrollment.

Contraception Guidance:

| |
|--|
| CONTRACEPTIVES ^a ALLOWED DURING THE STUDY INCLUDE: |
| Highly Effective Methods^b That Have Low User Dependency |
| 
 • Implantable progestogen-only hormone contraception associated with inhibition of ovulation^c • Intrauterine device (IUD) • Intrauterine hormone-releasing system (IUS)^c • Bilateral tubal occlusion • Vasectomized partner • (Vasectomized partner is a highly effective contraceptive method provided that the partner is the sole sexual partner of the woman of childbearing potential and the absence of sperm has been confirmed. If not, an additional highly effective method of contraception should be used. Spermatogenesis cycle is approximately 90 days.) |
| Highly Effective Methods^b That Are User Dependent |
| 
 • Combined (estrogen- and progestogen-containing) hormonal contraception associated with inhibition of ovulation^c 
 ○ oral ○ intravaginal ○ transdermal ○ injectable • Progestogen-only hormone contraception associated with inhibition of ovulation^c 
 ○ oral ○ injectable • Sexual abstinence (Sexual abstinence is considered a highly effective method only if defined as refraining from heterosexual intercourse during the entire period of risk associated with the study intervention. The reliability of sexual abstinence needs to be evaluated in relation to the duration of the study and the preferred and usual lifestyle of the participant.) |

- a Contraceptive use by men or women should be consistent with local regulations regarding the use of contraceptive methods for those participating in clinical studies.
- b Failure rate of <1% per year when used consistently and correctly. Typical use failure rates differ from those when used consistently and correctly.
- c If locally required, in accordance with Clinical Trial Facilitation Group (CTFG) guidelines, acceptable contraceptive methods are limited to those which inhibit ovulation as the primary mode of action.

Note: Periodic abstinence (calendar, symptothermal, post-ovulation methods), withdrawal (coitus interruptus), spermicides only, and lactational amenorrhea method (LAM) are not acceptable methods of contraception for this study. Male condom and female condom should not be used together (due to risk of failure with friction).

Collection of Pregnancy Information

Male participants with partners who become pregnant

- The investigator will attempt to collect pregnancy information on any male participant's female partner who becomes pregnant while the male participant is in this study. This applies only to male participants who receive study intervention.
- After obtaining the necessary signed informed consent from the pregnant female partner directly, the investigator will record pregnancy information on the appropriate form and submit it to the sponsor within 24 hours of learning of the partner's pregnancy. The female partner will also be followed to determine the outcome of the pregnancy. Information on the status of the mother and child will be forwarded to the sponsor. Generally, the follow-up will be no longer than 6 to 8 weeks following the estimated delivery date. Any termination of the pregnancy will be reported regardless of fetal status (presence or absence of anomalies) or indication for the procedure.

Female Participants who become pregnant

- The investigator will collect pregnancy information on any female participant who becomes pregnant while participating in this study. Information will be recorded on the appropriate form and submitted to the sponsor within 24 hours of learning of a participant's pregnancy.
- The participant will be followed to determine the outcome of the pregnancy. The investigator will collect follow-up information on the participant and the neonate and the information will be forwarded to the sponsor. Generally, follow-up will not be required for longer than 6 to 8 weeks beyond the estimated delivery date. Any termination of pregnancy will be reported, regardless of fetal status (presence or absence of anomalies) or indication for the procedure.
- While pregnancy itself is not considered to be an AE or SAE, any pregnancy complication or elective termination of a pregnancy will be reported as an AE or SAE. A spontaneous abortion is always considered to be an SAE and will be reported as such. Any post-study pregnancy related SAE considered reasonably related to the study intervention by the investigator will be reported to the sponsor as described in Section 8.3.2. While the investigator is not obligated to actively seek this information in former study participants, he or she may learn of an SAE through spontaneous reporting.
- Any female participant who becomes pregnant while participating in the study will discontinue study intervention or be withdrawn from the study.

10.4. Appendix 4: Liver Safety: Suggested Actions and Follow-up Assessments

Selected tests may be obtained in the event of a treatment-emergent hepatic abnormality and may be required in follow-up with patients in consultation with the Lilly medical team. In general, the labs below should be sent at first occurrence of Grade ≥ 3 elevated hepatic lab increases (ALT, AST, or direct bilirubin). For subsequent occurrences, these labs may be repeated at the discretion of the investigator.

| Hepatic Safety Tests | |
|---|---|
| 
Hepatic Hematology^a Hemoglobin (HGB) Hematocrit (HCT) Erythrocytes (RBC) Leukocytes (WBC) Neutrophils^b Lymphocytes Monocytes Eosinophils Basophils Platelets (PLT)
 
Hepatic Chemistry^a Total bilirubin Direct bilirubin Alkaline phosphatase Alanine aminotransferase (ALT) Aspartate aminotransferase (AST) Gamma-glutamyl transferase (GGT) Creatine phosphokinase (CPK)
 | 
Haptoglobina^a
 
Hepatic Coagulation^a Prothrombin time (PT) Prothrombin time, INR
 
Hepatic Serologies^{a,c} Hepatitis A antibody, total Hepatitis A antibody, IgM Hepatitis B surface antigen Hepatitis B virus DNA^c Hepatitis B surface antibody Hepatitis B Core antibody Hepatitis C antibody Hepatitis C virus RNA PCR^c Hepatitis E antibody, IgG Hepatitis E antibody, IgM Hepatitis E virus RNA PCR^c
 
Recommended Autoimmune Serology Anti-nuclear antibody^a Anti-smooth muscle antibody^a Anti-actin antibody^a
 |

Abbreviations: CRF = case report form; IgG = immunoglobulin G; IgM = immunoglobulin M; INR = international normalized ratio; RBC = red blood cells; WBC = white blood cells.

- ^a Assayed by central laboratory.
- ^b Neutrophils reported by automated differential hematology instruments include both segmented and band forms. Whenever a manual differential is needed to report the neutrophils, the segmented and band forms should be added together and recorded on the CRF, unless the CRF specifically provides an entry field for bands.
- ^c Reflex/confirmation dependent on regulatory requirements and/or testing availability.

10.5. Appendix 5: Country-specific Requirements

10.5.1. Discontinuation of Inadvertently Enrolled Patients in the UK and Germany

If the sponsor or investigator identifies a participant who did not meet enrollment criteria and was inadvertently enrolled, then the participant should be discontinued from study treatment and safety follow up should be performed as outlined in Section 1.3 (Schedule of Activities), Section 8.3 (Adverse Events and Serious Adverse Events), and Section 8.2 (Safety Assessments) of the protocol.

10.6. Appendix 6: *RET* activating mutations in MTC

| Exon | RET mutation |
|---|--|
| 5 | V292M, G321R |
| 8 | A510V, E511K, C515S, C531R, G533C |
| 10 | V591I, R600Q, K603E/Q, Y606C, C609F/G/R/S/W/Y, C611F/G/R/S/W/Y, C618F/G/R/S/W/Y, C620F/G/R/S/W/Y |
| 11 | C630R/Y, D631Y, E632K, C634F/G/R/S/W/Y, S649L, K666E/M |
| 13 | E768D, R770Q, N777S, V778I, Q781R, L790F |
| 14 | V804L, V804M, Y806C, E819K, R833C, R844Q, R866W, M848T |
| 15 | L881V, A883F/S/T/V, R886W, S891A, S904F |
| 16 | S904C/F, G911D, R912P, M918T, E921K, S922P, T930M |
| Complex | D631del, E632-L633del, D898-E901del, E632-A639> HR |
| Other | Because the list of published activating RET mutations is constantly being updated, other mutations (e.g. other complex mutations, overlapping deletions, substitutions with different amino acids at the same site) may be eligible if a compelling rationale is provided by the Investigator and approved by the sponsor. |
| No other known validated MTC driver alteration(s). These include RAS or BRAF gene mutations and NTRK gene fusions. | |
| Mutation identified in a tumor, germline DNA or blood sample according to laboratory with CLIA, ISO/IEC, CAP, or similar certification, as long as a written Molecular Pathology Report is available and clearly asserts the presence of the referenced RET alteration (Dvorakova et al. 2008, Agrawal et al. 2013, Krampitz et al. 2014, Ji et al. 2015, Wells et al. 2015, Heilmann et al. 2016, Romei et al. 2016, Kato et al. 2017). | |

Abbreviations: CAP-College of American Pathologists; CLIA-Clinical Laboratory Improvement Amendments; ISO/IEC-International Organization for Standardization/Independent Ethics Committee; MTC-medullary thyroid cancer.

10.7. Appendix 7: Restricted and Prohibited Concomitant Medications

The table(s) below describes the drug class and associated medications that will be restricted or prohibited during the study treatment period.

This is not an all-inclusive list; in general, all strong and moderate CYP3A4 inhibitors, strong and moderate inducers of CYP3A4, sensitive CYP2C8 substrates, and protein pump inhibitors (PPI's) are restricted during the study treatment period. Agents known to cause QTc prolongation are prohibited in patients receiving selpercatinib or vandetanib during the study treatment period.

Note: Non-systemic (e.g., topical creams, eye drops, mouthwashes, etc.) applications of the following are permissible.

| Inhibitors of CYP3A4 | |
|--------------------------------------|--|
| Strong Inhibitors^a | Moderate Inhibitors^b |
| boceprevir | Amprenavir |
| clarithromycin | Atazanavir |
| conivaptan | Ciprofloxacin |
| grapefruit juice ^c | Darunavir |
| Indinavir | Diltiazem |
| Itraconazole | Erythromycin |
| Ketoconazole | Fluconazole |
| Lopinavir | Fosamprenavir |
| Mibefradil | Imatinib |
| Nefazodone | Verapamil |
| Nelfinavir | |
| Posaconazole | |
| Ritonavir | |
| Saquinavir | |
| Telaprevir | |
| Telithromycin | |
| Voriconazole | |

Abbreviations: AUC = area under the concentration versus time curve; CYP3A4 = cytochrome P450 3A4.

- a Increases the AUC of sensitive index substrates of a given metabolic pathway by ≥ 5 -fold.
- b Increases the AUC of sensitive index substrates of a given metabolic pathway by 2- to 5-fold.
- c When excessive amounts are consumed.

Inducers of CYP3A4**Strong Inducers^a**

Avasimibe
 Carbamazepine
 Enzalutamide
 Phenytoin
 Rifampin
 St John's wort

Moderate Inducers^b

Bosentan
 Efavirenz
 Etravirine
 Modafinil
 Nafcillin

Abbreviations: AUC-area under the concentration versus time curve; CYP3A4-cytochrome P450 3A4.

^a Decreases the AUC of the sensitive index substrates of a given metabolic pathway by $\geq 80\%$.

^b Decreases the AUC of the sensitive index substrates of a given metabolic pathway by 50–80%.

Sensitive CYP2C8 substrates

Repaglinide
 Dasabuvir
 Selexipag

Examples of Proton Pump Inhibitors (PPIs)

| | |
|--------------|-----------------|
| omeprazole | pantoprazole |
| esomeprazole | rabeprazole |
| lansoprazole | dexlansoprazole |

Note: The above lists are not exhaustive. See also:

<http://www.fda.gov/drugs/developmentapprovalprocess/developmentresources/druginteractionslabeling/ucm093664.htm>.

Examples of Agents Known to Cause QTc Prolongation

| | |
|----------------------------------|-------------------------------------|
| Amiodarone | ibogaine |
| Anagrelide | Ibutilide |
| Azithromycin | levofloxacin |
| Chloroquine | levomepromazine (methotrimeprazine) |
| Chlorpromazine | levosulpiride |
| Cilostazol | Methadone |
| Ciprofloxacin | moxifloxacin |
| Citalopram | Ondansetron |
| Clarithromycin | papaverine HCl (intracoronary) |
| Cocaine | Pentamidine |
| Disopyramide | Pimozide |
| Dofetilide | procainamide |
| domperidone | Propofol |
| Donepezil | Quinidine |
| Dronedarone | roxithromycin |
| Droperidol | Sevoflurane |
| Erythromycin | Sotalol |
| Escitalopram | sulpiride |
| Flecainide | sultopride |
| Fluconazole | terlipressin |
| halofantrine | terodiline |
| Haloperidol | Thioridazine |
| hydroquinidine, dihydroquinidine | |

Note: The above list is not exhaustive. Please refer to <https://www.crediblemeds.org/> for a current list of agents known to cause QTc prolongation as well as agents with a possible or conditional risk.

Examples of H2 blocking agents

| | |
|------------|------------|
| Famotidine | cimetidine |
| Ranitidine | nizatidine |

Note: The above lists are not exhaustive. See also:
<http://www.fda.gov/drugs/developmentapprovalprocess/developmentresources/druginteractionslabeling/ucm093664.htm>

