 21. Other malignancy unless nonmelanoma skin cancer, carcinoma in situ or malignancy diagnosed ≥ 2 years previously and not currently active. Patients receiving adjuvant hormone therapy for breast or prostate cancer with no evidence of disease are eligible. Participants with MEN2-associated pheochromocytoma are eligible if the pheochromocytoma is, in the opinion of the investigator, documented to be stable or has been resected (and patient has fully recovered from surgery).

Prior/Concomitant Therapy

22. Prior systemic treatment with kinase inhibitor(s) (Refer to Section 5.1, Inclusion Criterion 2b).
23. Are taking a concomitant medication that is known to cause QTc prolongation (for examples, see Appendix 7).

Prior/Concurrent Clinical Study Experience

24. Have participated, within the last 30 days (4 months for studies conducted in Japan; 3 months for studies conducted in the UK), in a clinical study involving an investigational product. If the previous investigational product has a long half-life, 5 half-lives or 30 days (4 months for studies conducted in Japan; 3 months for studies conducted in the UK) (whichever is longer) should have passed. Exceptions will be considered on a case by case basis by the Lilly medical team.

Other Exclusions

25. Life expectancy ≤ 3 months

26. Have a known hypersensitivity to any of the excipients of selpercatinib, cabozantinib, or vandetanib.

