6.5. Concomitant Therapy

Any medication or vaccine (including over-the-counter or prescription medicines, vitamins, and/or herbal supplements) that the participant is receiving at the time of enrollment or receives during the study must be recorded along with:

- Reason for use
- Dates of administration including start and end dates.

Patients receiving selpercatinib should avoid concomitant use of CYP2C8-sensitive substrates. If co-administration of a CYP2C8-sensitive substrate cannot be avoided, monitor patients for increased adverse reactions of these drugs.

Caution should be used when co-administration of a P-gp substrate (for example, fexofenadine, loperamide, and digoxin), MATE1 substrate (for example, metformin), or BCRP substrate (for example, sulfasalazine) cannot be avoided in patients receiving selpercatinib. Consider increased monitoring as appropriate. The concurrent use of drugs known to prolong QTc is prohibited (Appendix 7). Drugs with a possible or conditional risk should be avoided if possible. Patients eligible to receive vandetanib should refrain from sun exposure during and up to 4 months after discontinuation of treatment due to possible photosensitivity.

The Lilly medical team should be contacted if there are any questions regarding concomitant or prior therapy. Except as indicated in Section 6.1, patients are not allowed to receive concomitant systemic anti-cancer agents (including immunotherapy agents), hematopoietic growth factors for prophylaxis in C1, drugs with immunosuppressant properties (other than as listed in Section 6.5.4), or any other investigational agents. No new, alternative systemic anticancer therapy is allowed prior to documentation of PD in accordance with protocol specified disease response criteria. No surgical resection of tumor or radiation therapy is permitted except as described in Section 6.5.4.

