6.5.1. CYP3A4 Inducers or Inhibitors

For patients receiving selpercatinib: The concomitant use of the strong CYP3A4 inhibitors or inducers should be avoided. See Appendix 7.

If, during the study, patients require initiation of treatment with strong inhibitors or inducers of CYP3A4 for clinical reasons, investigators should consider increased monitoring for the development of new AEs.

Co-administration of selpercatinib with sensitive CYP3A4 substrates may increase their plasma concentrations, which may increase the incidence or severity of adverse reactions for sensitive substrates with narrow therapeutic windows.

For patients receiving cabozantinib: The concomitant use of strong inhibitors or inducers of CYP3A4 should be avoided. If strong CYP3A4 inhibitors cannot be avoided, the cabozantinib dose should be reduced by 20 mg daily; if the CYP3A4 inhibitor is to be discontinued, the regular dose cabozantinib should be resumed 2 to 3 days after discontinuation of the strong inhibitor. If strong CYP3A4 inducers cannot be avoided, the cabozantinib dose should be increased by 20 mg daily; if the CYP3A4 inducer is to be discontinued, resume the regular dose of cabozantinib 2-3 days after discontinuation of the strong inducer. See Appendix 7.

For patients receiving vandetanib: The concomitant use of strong inducers of CYP3A4 should be avoided. See Appendix 7.

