6.5.2. Agents That Alter Gastric Acidity (PPIs and H2 blockers)

Since selpercatinib absorption from the gastrointestinal tract may be impacted by stomach acidity, concomitant use of pH-altering agents require additional instructions for patients randomly assigned to treatment arm A.

Avoid concomitant use of a PPI, H2 receptor antagonist, or a locally-acting antacid with selpercatinib. If concomitant use cannot be avoided,

- Take selpercatinib with food (at least 400 calories) when co-administered with a PPI.
- Take selpercatinib 2 hours before or 10 hours after administration of an H2 receptor antagonist.
- Take selpercatinib 2 hours before or 2 hours after administration of a locally-acting antacid.

There are no restrictions on PPI or H2 blocker use for patients randomized to the control arm and who are receiving cabozantinib or vandetanib.

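### Section 6.5 and Appendix 7 give different concomitant-medication rules: QTc-prolonging drugs with cabozantinib, PPIs in the control arm and, less sharply, CYP3A4 and CYP2C8 agents

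*Protocol*

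**What the plan says.** **QTc-prolonging drugs.** Section 6.5 says "The concurrent use of drugs known to prolong QTc is prohibited (Appendix 7"), with no study drug named. Appendix 7, the place cited, says: "Agents known to cause QTc prolongation are prohibited in patients receiving selpercatinib or vandetanib during the study treatment period". Its list of example agents includes ondansetron, citalopram and fluconazole.

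**Proton pump inhibitors.** Appendix 7 says that "in general, all strong and moderate CYP3A4 inhibitors, strong and moderate inducers of CYP3A4, sensitive CYP2C8 substrates, and protein pump inhibitors (PPI's) are restricted" during study treatment, again with no arm named. Section 6.5.2 asks that PPIs be avoided with selpercatinib, then says: "There are no restrictions on PPI or H2 blocker use for patients randomized to the control arm and who are receiving cabozantinib or vandetanib".

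**CYP3A4 agents.** The Appendix 7 sentence covers strong and moderate inhibitors and inducers. Section 6.5.1 names strong inhibitors and inducers for selpercatinib and for cabozantinib. For vandetanib it is narrower: "For patients receiving vandetanib: The concomitant use of strong inducers of CYP3A4 should be avoided". Each of the three paragraphs sends the reader to Appendix 7.

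**CYP2C8 substrates.** Section 6.5 addresses its rule to patients on selpercatinib. Appendix 7 puts sensitive substrates in the same general restriction and names no study drug.

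**The concern.** Section 6.5 and its subsections are what a site reads when prescribing, and Appendix 7 is the reference they point to. Where the two differ, two sites can follow the protocol in good faith and manage the same patient differently. A patient on cabozantinib who needs an antiemetic could be given ondansetron at one site and refused it at another. A control patient on a PPI could be treated as unrestricted under Section 6.5.2 and as restricted under Appendix 7.

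Monitoring has the same difficulty. The same prescription can be recorded as a deviation or as permitted use, depending on the page consulted. SAP Section 8.2.1 places the list of important protocol deviations in a separate management plan, and that list determines who leaves the per-protocol population. Whether it counts restricted or prohibited medication cannot be seen from these documents.

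**Working it through.** No arithmetic decides this point. The check sets the current texts side by side for each study drug.

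| Class | Study drug | Section 6.5 and subsections | Appendix 7 | Result |
|---|---|---|---|---|
| QTc-prolonging | selpercatinib | prohibited (no drug named) | prohibited | agree |
| QTc-prolonging | vandetanib | prohibited (no drug named) | prohibited | agree |
| QTc-prolonging | cabozantinib | prohibited (no drug named) | not named | **inconsistent** |
| PPI | selpercatinib | avoid, with conditions if unavoidable | restricted | compatible |
| PPI | cabozantinib | no restriction | restricted | **inconsistent** |
| PPI | vandetanib | no restriction | restricted | **inconsistent** |
| Moderate CYP3A4 inhibitors and inducers | all three | silent | restricted | mismatch by silence |
| Strong CYP3A4 inhibitors | vandetanib | silent | restricted | mismatch by silence |
| Sensitive CYP2C8 substrates | cabozantinib, vandetanib | rule addressed to selpercatinib only | restricted | mismatch in scope |

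Reading down the table:

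1. The QTc inconsistency concerns one drug. Both texts prohibit listed agents with selpercatinib and vandetanib, so ondansetron is in doubt for cabozantinib patients only.
2. The PPI inconsistency covers both control drugs. It is the most direct of the set, because one text imposes a restriction and the other expressly says there is none.
3. The CYP3A4 difference is mainly one of potency class. For moderate agents it runs across all three study drugs, Arm A included. Section 6.5.1 is silent on moderate agents and does not permit them.
4. Appendix 7 uses *restricted* beside *prohibited* without defining it. Section 6.5 and its subsections speak of avoiding or prohibiting. The terms cannot be mapped onto one another from the text.
5. Crossover needs its own entry. Section 6.5.2 introduces its instructions for patients assigned to Arm A, and its no-restriction sentence is for control patients who are taking cabozantinib or vandetanib. A control patient who has crossed over to selpercatinib is reached only by the sentence that names the drug.

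**How many patients come under the wording.** At 2:1 randomization the control arm is one third of the total: 250 / 3 ≈ 83 patients, or 400 / 3 ≈ 133 at the maximum enrolment. These are the patients to whom the conflicting PPI text applies. The cabozantinib share is not planned, since the control drug is the physician's choice, so the number under the QTc inconsistency lies somewhere between 0 and those totals. The documents give no expected use of PPIs or QTc-listed drugs, so the number who would actually meet the conflict cannot be derived.

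**The case against.** The best defence is that the texts can be reconciled. The QTc sentence in Section 6.5 cites Appendix 7 and follows sentences about selpercatinib, so it might simply adopt the appendix's scope. For PPIs, a specific statement about the control arm would ordinarily override a general one that says *restricted* and not prohibited. On CYP3A4, silence in Section 6.5.1 is not permission. Section 6.5 also directs questions on concomitant therapy to the sponsor's medical team.

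Part of this stands. The CYP3A4 and CYP2C8 items are lesser mismatches, not direct contradictions, and the medical-team contact is a real mitigation, though only for a site that notices the problem. The reconciling readings are plausible but nowhere stated. Other sentences in Section 6.5 name a study drug when they mean one and the QTc sentence does not. No rule of precedence between text and appendix is given.

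Three other passages might be taken to strengthen the case, and they do not.

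- **Section 6.5.4** has a proviso about the prohibited list, but it attaches to standard medications continued from the previous 28 days. It does not govern an antiemetic newly started on treatment.
- **Exclusion criterion 23** ("Are taking a concomitant medication that is known to cause QTc prolongation") operates before randomization, when every entrant may be assigned selpercatinib. An entry rule that ignores arm is compatible with an on-treatment rule that depends on the drug.
- **Section 6.6** deals with QTcF above 500 msec on cabozantinib. It says nothing about which concomitant drugs are barred.

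**Conclusion.** The protocol is inconsistent as written on two operative rules: QTc-prolonging drugs with cabozantinib, and PPIs with either control drug. It has two lesser mismatches, on CYP3A4 potency class and on the scope of the CYP2C8 rule. The passages must be reconciled. The conclusion rests on the current text alone and takes no view on which rule is clinically right.

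A reader might infer that uneven symptom control in the control arm biases FACT-GP5, which is a type I error-controlled key secondary endpoint. The documents do not support that. Any effect is unsized and could run either way: withholding PPIs could raise control-arm bother, and allowing more antiemetics could lower it. The item asks about side effects of treatment, which untreated reflux need not be. No error-rate problem follows, and nothing here touches the primary PFS analysis.

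Nor does it follow that all 83 or so control patients are affected. That figure counts patients under the wording, not patients who need one of these drugs.

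The correction should be made because it bears on patient safety and on the consistent recording of deviations, and because it is cheap.

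**What to change.** Reconcile Sections 6.5, 6.5.1 and 6.5.2 with Appendix 7 so that each drug class has one stated status for each study drug. A single table in Appendix 7 would do this:

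- **Columns:** selpercatinib, cabozantinib, vandetanib, and selpercatinib after crossover.
- **Rows:** QTc-prolonging agents; PPIs and H2 blockers; strong and moderate CYP3A4 inhibitors and inducers, shown separately; sensitive CYP2C8 substrates.
- **Entries:** a fixed set of terms, with *restricted* either defined or replaced.

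The body text should then refer to the table and not restate the rules, and protocol deviations for concomitant medication should be classified from the same table. The sponsor's medical team decides each entry.

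The cost is one replacement table with matching edits in the next amendment, and a memo to sites. No new data are needed, since concomitant medication is already recorded.
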